1. Study Protocol

A Phase II open label, single arm, single centre clinical study on the effect of a moisturiser containing tocotrienol rich composition on mild to moderate atopic dermatitis in children

2. Principal investigator/ Site Principal Investigator:

[name] [name], Universiti Putra Malaysia

3. Co-investigators

[name]. [name], Universiti Putra Malaysia [name] [name], Lipidware Sdn. Bhd [name] [name], Lipidware Sdn. Bhd

4. Introduction

Natural extracts and actives are highly sought after for the management of skin disorders especially those that requires long-term, consistent usage: some to boost skin health, and some to prevent disturbing undesirable symptoms, including dry, itchy skin. Eczema is such long-term condition that causes the skin to become itchy, red, dry and cracked. The condition most often develops before a child's first birthday, although it can also appear in adults for the first time. Eczema symptoms vary between having small patches of dry skin, and having widespread inflamed, red skin. Earlier, it has been reported that patients could relieve signs of atopic dermatitis by taking daily Vitamin E supplements. It is reported that Vitamin E supports healthy skin due to its antioxidant activity besides working at the immune level to benefit the skin. Vitamin E specifically those from palm oil, is Generally Regarded as Safe (GRAS) (USFDA GRAS GRN 307). There are two types of Vitamin E i.e. tocopherol and tocotrienol where the latter has been found to be almost 60 times more potent an antioxidant than the former. Till date, study of Vitamin E, especially tocotrienol concentrated, as topical moisturiser for the management of atopic dermatitis is scarce. This study aimed to assess the effectiveness and safety of a moisturiser containing tocotrienol rich composition (REMDII[®] Sensitive, Malaysia) on children with mild-to-moderate atopic dermatitis in a period of 12 weeks. The endpoints of the study include changes in the severity of atopic dermatitis based on Investigator Global Assessment (IGA) score,

Scoring Atopic Dermatitis Index (SCORAD), Infant Dermatology Life Quality Index (IDLQI), Patient-oriented Scoring Atopic Dermatitis Index (PO-SCORAD) and pruritus score. Expectedly, REMDII[®] Sensitive would significantly improve the severity of atopic dermatitis in children.

5. Research Question

- a) Could moisturiser with tocotrienol rich composition (REMDII[®] Sensitive, Malaysia) improve severity of atopic dermatitis of children with mild to moderate atopic dermatitis?
- b) What is the extend of baseline changes in IGA, SCORAD, IDLQI, PO-SCORAD, HR-USI, TEWL, skin color and pruritus score in children upon usage of REMDII[®] Sensitive?
- c) How well would children tolerate REMDII[®] Sensitive?

6. Research objectives and hypotheses

General objective

To assess the effectiveness and safety of a moisturiser containing tocotrienol rich composition (REMDII[®] Sensitive, Malaysia) on children with mild-to-moderate atopic dermatitis.

Specific objectives

- To assess the effectiveness and safety of REMDII[®] Sensitive as a supplement in mild-to-moderate atopic dermatitis in children based on the changes of IGA score and SCORAD.
- To assess correlation between patient-assessed PO-SCORAD and clinicianassessed IGA and SCORAD in children after 12 weeks of treatment using REMDII[®] Sensitive.
- To assess the changes in IDLQI.
- To assess the changes in patients' assessment of pruritus (based on a 100 mm Visual Analogue Scale and 0-3 ordinal scale).

- To assess the changes in skin properties, specifically high resolution ultrasound skin imaging (HR-USI), transepidermal water loss (TEWL) and skin color in children before and after application of REMDII[®] Sensitive.
- To assess the frequency of need for rescue medication in the event of an atopic dermatitis flare.

Hypotheses

Null: REMDII[®] Sensitive does not improve severity of atopic dermatitis of children with mild to moderate atopic dermatitis.

Alternative: REMDII[®] Sensitive significantly improves severity of atopic dermatitis of children with mild to moderate atopic dermatitis.

7. Literature review

Eczema is a general term used to describe numerous forms of epidermal inflammation or irritation that occurs regardless of gender, race and age. Among the various types of eczema, the most prevalent type is atopic dermatitis (AD). Currently, the prevalence rate of AD in children and adolescents was 15.0-20.0%, regardless of regions (Asher et al., 2006; Baek et al., 2013). Eczema poses significant impact and inconveniences to the patients' quality of life and health-care resources, mainly because of sleep deprivation and demoted self-esteemed (due to itchiness, scarring, lichenification, peer pressure and time to care), that would in turn affects the child's growth and development.

AD is a complex disease, and genetics has recently been shown to be an important risk factor for AD, and the strongest association so far with the gene encoding filaggrin has raised the recent interest in the role of skin barrier impairment in the development of AD (Nutten, 2015). There is no cure for AD yet, although a wide range of treatments have been introduced to ease the symptoms and keep the skin conditions under control. The most common treatment of AD involves the use of corticosteroids and in certain cases, immunosuppressants – both of which need strict monitoring of medical professionals and carelessness of application would lead to negative irreversible consequences (Liu et al.,

2013). Therefore, prevention is still regarded as the best management strategy for AD, some of the opinion that prevention should start as soon as possible (possibly even in utero), targeting both skin barrier, immune/ allergy and environmental aspects (Nutten, 2015). The application of emollients and moisturisers to maintain skin hydration is still by far the safest and most basic therapy of treating AD. Often, humectants and pharmacological compounds are also added into moisturisers or emollients as parts of AD skin treatment.

Nutten (2015) found that environmental factors and specifically exposure to microbes are increasingly recognized to play a role in the development of AD. In this finding, the sole use of moisturisers, in the absence of sufficient topical anti-inflammatory therapy, would involve a significant concern over the risk of microbial infection. In addition, direct use of emollients on inflamed acute patches is poorly tolerated and may lead to stinging pain. Topical corticosteroids and calcineurin inhibitors are still the standard choice for topical anti-inflammatory therapy despite their risk of carcinogenicity (Arellano et al., 2009; Arellano, Wentworth, Arana, Fernández, & Paul, 2007). Although topical corticosteroids are useful in suppressing skin inflammation, long period of usage (which is usually the case to maintain a reasonable quality of life) are more likely to cause skin atrophy which further aggravates skin barrier functions. Consequently, there is still a need for a moisturiser containing natural anti-inflammatory properties with minimal or no side effect for the prevention or treatment of skin disorders.

Children's skin is very delicate. The need for a more natural topical moisturiser with maximal efficacy and minimal side effects and irritation potentials is highly demanded by the public. The latest search for a worldwide listing of AD medical research trials actively recruiting patient volunteers on CenterWatch yielded only 91 interventional studies and 25 observational studies where 14 are labeled as Phase I trials, 36 Phase IIs, 41 Phase IIIs, 10 Phase IVs, 3 Phase I/IIs, 4 Phase II/IIIs and the rest unknown (https://www.centerwatch.com/clinical-trials/listings/condition/695/atopic-dermatitis/). In Malaysia, only 3 dermatological-categorized clinical trials where reported for the year 2012-2017 (NPRA, 2018). Choices for clinically tested OTC moisturiser are scarce as compared to non-tested cosmetic grade moisturisers. Lai, Tan, Lai, and Khong (2016) have recently derived a natural antioxidant and preservative with selective antimicrobial

properties to hygiene-related pathogens from palm oil. The natural bioactive was found to exhibit higher and broader antimicrobial activity compared to virgin coconut oil and extra virgin olive oil *in vitro*. One of the apparent advantages of this active is the superior stability of the Vitamin E in an accelerated shelf life study (Figure 1).

Figure 1. Retention of total Vitamin E content (α -tocopherol, α -tocotrienol, β -tocopherol, β -tocotrienol) of processed active at different temperatures.

The IP of this study is a topical moisturiser containing tocotrienol rich composition from plant source (REMDII[®] Sensitive, Malaysia). REMDII[®] Sensitive contains both tocopherol (α , β , $\gamma \& \delta$) and tocotrienol (α , β , $\gamma \& \delta$). Serbinova, Kagan, Han, and Packer (1991) showed that tocotrienols can be 40-60 times more potent as antioxidant than tocopherols. Vitamin E especially palm-based has been proven repeated to exhibit no adverse effects in both normal as well as vulnerable subjects while potentially poses significantly high benefits with very low risks (Argyriou et al., 2006; Kappus & Diplock, 1992; Meydani et al., 1998). In a prospective, randomised, double-blinded trial involving 84 post-surgical subjects, no significant adverse effect was observed up to the dosage of 5% topical tocotrienol, applied twice-daily over 4 months post-surgery (Khoo et al., 2011). In another study, Hasan, Idris, Gani, and Basri (2018) concluded that palm tocotrienol rich fraction has no indication of irritancy to both ocular and dermal tissues and could be

classified as Category 1 according to United Nations Globally Harmonised System of Classification and labelling of Chemicals. Hasan, Ismail, and Ahmad (2008) also concluded that palm tocotrienol rich fraction do not induce any cutaneous reactions including irritation and dermatitis and it is safe to be used for topical applications. REMDII[®] Sensitive has been registered to the National Pharmaceutical Regulatory Agency (NPRA), Kementerian Kesihatan Malaysia with the notification number NOT181000506K, tested for its product stability and certified halal. Thus, subject could benefits freedom of better accessibility to the Vitamin E in the IP with lesser risk on exposure to unknown degradatory products resulted from product instability. Besides, REMDII[®] Sensitive has also been tested to have low risk of adverse effect ($LC_{50} = >5000$ $\mu g/mL$) in vivo.

As a topical cosmetic or over-the-counter product, Vitamin E has been used in product concentration of 1%-5% (w/w) for almost half a century. The lipophilic nature of vitamin E makes it suitable for topical application and percutaneous absorption through the skin (Krol, Kramer-Stickland, & Liebler, 2000; Lin et al., 2003). When topically applied, vitamin E has been shown to hydrate the stratum corneum (SC), improve skin hydration and improve water-binding capacity (Ismail, Affandi Yusoff, & Hashim, 2009; Manela-Azulay & Bagatin, 2009). Topical vitamin E was also found to significantly reduced postoperative pain in a prospective randomized clinical trial involving 60 patients (Ruiz-Tovar et al., 2016). Thiele, Hsieh, and Ekanayake-Mudiyanselage (2005) summarised that Vitamin E could be considered an effective ingredient for imparting skin protection and treating atopic dermatitis (AD) based on experimental evidences suggesting that topical and oral vitamin E has anticarcinogenic, photoprotective, and skin barrier-stabilizing properties. In a 2015 randomized, controlled, double-blind, single center study involving 44 patients with mild to moderate AD in the perioral/periocular area and/or the neck, Patrizi et al. (2016) noted a significantly more rapid reduction in affected surface area with an emollient containing Vitamin E, compared with placebo; the product was found to be well tolerated and safe as well as effective for mild to moderate AD. Maarouf, Vaughn, and Shi (2018) also agrees that topical Vitamin E formulations appear to provide some benefit to AD individuals. In addition, Yap (2018) also showed that tocotrienol rich fraction is an effective anti-inflammatory agent that is safe to be applied daily. As nitric oxide (NO) has been shown to be involved in the pathogenesis of vasodilation and erythema in atopic dermatitis (Taniuchi et al., 2001), REMDII[®] Sensitive could be as potential product with potential in the management of AD. REMDII[®] Sensitive is tested to have inhibited ~50% NO level in vivo, slightly lower to ~60% NO inhibition activity of hydrocortisone 1% (w/w) (Hydrocortisone[®] Cream, Xepa-Soul Pattinson) *in vivo* (p>0.05).

In a study involving 13 human subjects, Ekanayake-Mudiyanselage et al. (2005) studied the effect of applying a Vitamin E-enriched rinse-off product and found that application of Vitamin E, even in rinse-off products, raised Vitamin E levels in human skin, which remained consistent for at least 24 hours, as opposed to the reduced finding of Vitamin E in the Vitamin E-free vehicle control group. The product also significantly inhibited photo-oxidation of squalene. Foote et al. (2009) findings also agrees to the elevation of Vitamin E level in human subject's skin upon application of Vitamin E containing cream and further proved the chemoprevention properties of the topical Vitamin E via reductions in polyamine metabolism which is consistent with the reductions in tumorigenesis potential. Further, Julianto, Pereira, Yuen, and Majid (2011) demonstrated that the mean droplet sizes of nanoemulsion hydrogel containing palm to cotrienol extract affect skin penetration and consequently the systemic bioavailability of δ -, γ -, and α tocotrienols, Nanoemulsion with smaller size was reported to have significantly heightened bioavailability of δ -tocotrienol. In agreement to this, total Vitamin E in a moisturizer with Vitamin E nanoemulsion (REMDII[®] Sensitive, Malaysia) was also observed to has significantly higher absorption in faster time compared to one with Vitamin E emulsion.

The proactive properties of Vitamin E to skin health promoting have widely been reported to be contributed by its antioxidative activity. Hayashi et al. (2012) demonstrated that lipid peroxidation in the skin and serum is significantly proportional to symptoms of atopic dermatitis and inflammation. Weber et al. (1997) found that tocotrienol rich fraction readily penetrate the skin of hairless mice and are protective against oxidative stress in vivo. Palm tocotrienol has also been demonstrated to promote wound healing by increasing superoxidase dismutase (SOD), catalase and glutathione (GSH) gene regulation (Shahrim, Omar, Zainal, & Hasan, 2016). Ex vivo study of tocotrienol against H₂O₂-induced oxidative stress found that the vitamin protects and prevents oxidation damages to the skin by upregulating of *COL1* and *COLIII* genes and increase in total collagen synthesis (Makpol,

Jam, Yusof, & Ngah, 2011). Anti-inflammatory properties of palm derived Vitamin E has been confirmed and it is reported to be caused by reducing pro-inflammatory cytokines, specifically IL-6, IL-8 and COX-2 in skin cells (Yap, 2018). As effective moisturization of the skin is a compulsory exercise for AD patients, Vitamin E played a role in improving AD by significantly increasing skin hydration and skin elasticity, while decreasing skin roughness in human subjects (Ismail et al., 2009). Besides, Tsuduki, Kuriyama, Nakagawa, and Miyazawa (2013) also found that tocotrienols reduces AD by suppressing degranulation of mast cells in vivo and tocotrienols' reduction of dermal inflammation follow similar mechanism as it's UV-B protection activity. Kapun et al. (2014) found that Vitamin E significantly improves atopic dermatitis in canine subjects due to improvements of oxidative stress.

Vitamin E has been attributed to positive properties especially to the skin. However, there is little clinical data on the effect of tocotrienol onto children's skin health especially in the treatment of AD. Therefore, the general aims of this study are:

- (1) To evaluate the efficacy of REMDII[®] Sensitive in treating AD topically;
- (2) To evaluate the effect of REMDII[®] Sensitive on skin properties, especially on skin ultrasound properties, skin color and transepidermal water loss;
- (3) To evaluate the safety of a REMDII[®] Sensitive in treating AD topically;
- (4) To evaluate if the usage of REMDII[®] Sensitive improves the quality of life in patients with AD.

8. Conceptual framework

Figure 2. Study outline

9. Research Methodology

9.1 Study Type and Design

9.1.1 Study design

A Phase 2, single arm, open label, single-centre trial will be conducted at Hospital Pengajar UPM, [name] and Lipidware Sdn. Bhd. Participants fulfilling the eligibility criteria will be selected. Each participant will be examined for signs and symptoms of AD before and after using REMDII[®] Sensitive. Figure 2 shows the outline of the study.

9.1.2 Investigative product (IP)

Subjects will be provided with REMDII[®] Sensitive throughout the duration of the study.

9.1.3 Endpoints

Primary endpoint: Change from baseline the severity of atopic dermatitis – IGA score.

Secondary endpoints:

- Changes in SCORAD
- Changes from baseline the
 - IDQOL & CDLQI
 - PO-SCORAD
 - Pruritus score (VAS/ ordinal)
 - Frequency of rescue treatment needed
 - High resolution ultrasound skin-imaging (HR-USI), skin color & Transepidermal Water Loss (TEWL)
- Correlation between SCORAD index and PO-SCORAD or IDLQI at each baseline and follow-up visit and absolute changes from baseline.
- Efficacy and safety assessment of the study product.

9.1.4 Study Population

Children (1 month – 12 years old) will be recruited through three routes i.e. patients who see the trial advertisements on bulletins made available in UPM (specifically Pusat Kesihatan Universiti, Hospital Pengajar UPM's Family Medicine Clinic, Medical Specialist Clinic, or Paediatric Clinic) that will contact the sponsor voluntarily; Patients who see the trial advertisements in social media, specifically Malaysia Eczema Support Community on Facebook, that will contact the sponsor voluntarily; and Patients who obtained words of mouth of the trial that will contact the sponsor voluntarily during the period of 1 July 2019 – 30 August 2019.

9.1.5 Inclusion Criteria

- **9.1.5.1** Male and female ages 1 month to 12 years with a diagnosis of atopic dermatitis based on UK Working Party Criteria of Atopic Dermatitis (Williams, Jburney, Pembroke, Hay, & Party, 1994).
- **9.1.5.2** Individuals with IGA score of at least mild (IGA= 2) or moderate (IGA= 3) and have at least 5% of body surface area affected during the inclusion time.
- **9.1.5.3** Individuals with a carer reported pruritus score based on VAS of at least 40 mm and above.
- **9.1.5.4** Individuals with no other chronic health condition other than atopic dermatitis e.g. asthma, allergic rhinitis or allergy.
- **9.1.5.5** Individuals with no objection towards use of topical corticosteroids as prescribed by attending medical officer during the study.
- **9.1.5.6** Written informed consent for participation in the trial.

9.1.6 Exclusion Criteria

- **9.1.6.1** Individuals with confounding skin diseases other than atopic dermatitis in the affected area which could interfere with assessment of treatment (e.g. psoriasis, rosacea, erythroderma, ichthyosis, acne, Netherton's syndrome, scabies, seborrheic dermatitis, and cutaneous lymphoma).
- **9.1.6.2** Individuals with severe atopic dermatitis (IGA = 4).
- 9.1.6.3 Individuals with active ongoing secondary infection of atopic dermatitis.
- **9.1.6.4** Individuals with any physical attributes or skin conditions that might interfere with the clear visual or instrumental assessments (i.e. cuts, sunburn, birth marks, tattoos, extensive scarring, excessive hair growth or acne).
- **9.1.6.5** Individuals with diabetes, severe liver disability (2.5-fold the normal high range value for ALT, AST) or severe renal disability (sCr > 2.0 mg/dl).
- **9.1.6.6** Individuals with immunodeficiency disorder or infectious disease (e.g. hepatitis, tuberculosis, HIV or AIDS, lupus rheumatoid arthritis.

- **9.1.6.7** Subjects who are not keen to start on corticosteroid on screening, despite informing that it is the first line treatment option according to the National Atopic Dermatitis guideline.
- **9.1.6.8** Use of other topical or systemic medications that could affect the course of their atopic dermatitis during the study period (except inhaled steroids and/or stable antihistamines for asthma or allergies for the past 30 days).
- **9.1.6.9** Use of steroids, oral antibiotics, immunosuppressants, other systemic treatments (i.e. retinoids, methotrexate, cyclosporine, hydroxycarbamide (hydroxyurea) and azathioprine) or physical therapy (i.e excimer laser, NBUVB, or PUVA) that could affect AD within 30 days or 5 half- lives.
- 9.1.6.10 History of drug abuse.
- **9.1.6.11** Hypersensitivity to Vitamin A, Vitamin C, Vitamin E or oil palm derived products.
- **9.1.6.12** Poorly controlled bronchial asthma, as mentioned according to GINA guideline.
- **9.1.6.13** Individuals with any other condition or factor the Investigator or their duly assigned representative believes may affect the ability of the subject to complete the study or the interpretation.

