9.1.10 Study Visits and Procedures

- 9.1.10.1 Subjects who are eligible to take part in this trial will need to attend to the study site for a total of 5 compulsory visits, as illustrated in Fig. 3.
- 9.1.10.2 During the screening/baseline visit, it will take about 1 hours where the investigators will take note of the subjects conditions for evaluation of study acceptability.
- 9.1.10.3 Prior to any baseline measurement, the correct usage of the cream will be explained by the investigator and the investigator's team. Subjects will be required to apply at least 1 fingertip unit to 2% body surface area. The subjects will receive treatment with the IP for topical application for 3 times a day for 12 weeks (according to the guideline that emphasize the important of using sufficient emollient).
- 9.1.10.4 Subjects will be provided with non-soap-based shower product (REMDII® Calming Body Wash, Malaysia) for subject's shower purpose throughout

the study. Subjects should avoid the usage of soap-based products throughout the study.

- 9.1.10.5 Subjects will also be provided with a diary, for recording of any application of rescue treatment and deviation from the study protocols.
- 9.1.10.6 Subjects who have flare up, will be managed using hydrocortisone 1% cream for a duration of 7 days. Those who are not responding to hydrocortisone end of 7 days will be prescribed with clobetasone butyrate 0.05% cream for additional 7 days. Those who doesn't respond to the treatment shall be withdrawn. However, subjects need to record the application in the provided diary. As well, any deviation or illness that occurs during the study will need to be recorded in the same diary as well.
- 9.1.10.7 Those who acquired secondary bacterial infection will be treated with a week of cloxacillin (50-100mg/kg/day po in 4 divided dose). For those who are above 20kg, will receive the usual adult dose.
- 9.1.10.8 In patients with penicillin allergy will be given a week of erythromycin ethylsuccinate at a dose of 30mg/kg/day in divided dose (up to a max 2gm/day).
- 9.1.10.9 Patients who have eczema herpeticum will received a week of oral acyclovir, in which subjects 1 month till 2 years will receive 100mg 5×/day; while subjects age 2 to 12 years old will received 200mg 5×/day dosage.
- 9.1.10.10After the explanation of the "Dos and Don'ts" to the guardians/parents, baseline measurement of atopic dermatitis severity of subjects using SCORAD index will be conducted.

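### The protocol leaves open whether children start a corticosteroid at the screening/baseline visit, and its single-arm before-after comparison would count any such steroid effect as product improvement

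*Protocol*

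**What the plan says.** Five places in the protocol bear on corticosteroid use.

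- **Exclusion 9.1.6.7** removes "Subjects who are not keen to start on corticosteroid on screening, despite informing that it is the first line treatment option". It speaks of starting, and of screening as the time.
- **Inclusion 9.1.5.5** asks for "Individuals with no objection towards use of topical corticosteroids as prescribed by attending medical officer during the study". No flare condition is attached.
- **Procedure 9.1.10.6** says "Subjects who have flare up, will be managed using hydrocortisone 1% cream for a duration of 7 days", with a second-step cream for non-responders.
- **Rescue objective (section 6):** "To assess the frequency of need for rescue medication in the event of an atopic dermatitis flare".
- **Exclusion 9.1.6.8** bars "Use of other topical or systemic medications that could affect the course of their atopic dermatitis during the study period", and 9.1.7.5 withdraws children who use a forbidden medication.

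On design, 9.1.1 states "A Phase 2, single arm, open label, single-centre trial will be conducted". The primary endpoint (9.1.3) is change from baseline in IGA. Under 9.1.10.2 screening and baseline are one visit, and 9.1.10.10 places the baseline SCORAD measurement there. Section 10 compares baseline with follow-up visits and does not mention steroid use.

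**The concern.** An investigator reading 9.1.6.7 with 9.1.5.5 could prescribe a corticosteroid at the screening/baseline visit and believe the protocol expects it. An investigator reading 9.1.10.6 with the rescue objective could hold it back until a flare. Both readings are reasonable, and they produce different trials.

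Under the first reading the steroid begins at about the time the baseline scores are taken, so almost all of its effect falls after baseline. With no comparator, that effect enters the change from baseline for IGA, SCORAD, pruritus and quality of life alike. Sections 6 and 11 would then credit it to the moisturiser. What is at stake is the attribution of every efficacy result. If practice varies between investigators or families, the size of the mixture would not be known either.

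**Working it through.** **Step 1. Passages side by side.**

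| Place | Role of corticosteroid | Start at entry? |
|---|---|---|
| 9.1.6.7 | First-line; the unwilling are excluded at screening | Suggested by the wording, not ordered |
| 9.1.5.5 | As the medical officer prescribes during the study | Allowed |
| 9.1.10.6 | Management of a flare | Not mentioned |
| Section 6, rescue objective | Rescue in a flare | Not mentioned |
| 9.1.6.8 and 9.1.7.5 | Other medication affecting the dermatitis is barred; forbidden medication leads to withdrawal | Unclear whether these reach a steroid prescribed at entry |
| 9.1.10.2 to 9.1.10.17 | Visit steps | No step dispenses a steroid at baseline |

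The text therefore permits a steroid at entry without requiring it. Exclusion 9.1.6.9 ("Use of steroids, oral antibiotics, immunosuppressants, other systemic treatments" and so on, within 30 days or 5 half-lives) looks back before entry and conflicts with none of these. Its only relevance is that children arrive recently steroid-free, so any steroid begun at entry is newly begun.

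**Step 2. The plan's own figure.** Section 9.1.8 uses a SCORAD difference of 10 and an SD of 13.576:

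n = 2 × (1.96 + 0.84)² × 13.576² / 10² = 28.90

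The protocol prints 28.932. Both round up to 29, and 29 / 0.90 = 32.2, rounded up to 33. The total of 33 reproduces and is not in dispute.

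**Step 3. Illustration.** The protocol gives no IGA effect size or SD, so SCORAD has to serve. Assumptions:

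- the product has no effect;
- steroid begun at entry moves the mean change by s points, where s = (steroid effect) × (share of children starting);
- a one-sample t test of the change is used, two-sided at 5%, with n = 33;
- the SD of change is 13.576, with 10 and 19.2 as the range (19.2 = 13.576 × √2, the value if the two visits were uncorrelated).

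Neither s nor the SD of change is given in the protocol.

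The noncentrality is s / (SD / √n). For s = 5 and SD 13.576, the standard error is 13.576 / √33 = 2.363 and the noncentrality is 5 / 2.363 = 2.12. With a critical value of 2.037 on 32 degrees of freedom, the rejection probability is 0.54.

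| Mean shift s | SD 10 | SD 13.576 | SD 19.2 |
|---|---|---|---|
| 1.5 | 0.13 | 0.09 | 0.07 |
| 2.5 | 0.29 | 0.18 | 0.11 |
| 3 | 0.39 | 0.23 | 0.14 |
| 5 | 0.80 | 0.54 | 0.31 |
| 10 | >0.99 | 0.98 | 0.83 |

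With 29 completers, s = 5 and SD 13.576, the figure is 0.48. With no steroid shift it is 0.05 throughout. A shift of 5 could come from a 10-point effect in half the children; 1.5 could come from a 5-point effect in 30% of them.

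**The case against.** The strongest reply is that 9.1.6.7 concerns attitude only: it screens out families who would refuse a steroid and pairs with 9.1.5.5. A site can exclude the unwilling, give hydrocortisone only when a child flares, and breach nothing. This stands. A reader might infer that the passages cannot both be followed, or that every enrolled child begins a steroid at entry. The documents support neither inference, and Figures 2 and 3, which might settle the matter, are not shown. What remains is that 9.1.5.5 already covers willingness during the study, and 9.1.6.7 adds starting and screening, so the other reading stays open.

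A reader might also see a conflict with 9.1.6.9 or 9.1.6.8. The first is a washout before entry. The second bars other medications, which can be read as those outside the protocol's own treatments. It needs clarifying but is not a contradiction.

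The illustration can fairly be called fragile. Effect, uptake and SD are assumed; the 10-point difference was chosen for sample size and says nothing about topical steroid in children. SCORAD is a secondary endpoint, and section 10 names ANOVA or Kruskal-Wallis for it. The flare courses in 9.1.10.6 are 7 days plus 7 days within 12 weeks, so an effect may not last to the final visit. All of this stands, and the rates are not estimates for this trial.

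Finally, a single-arm trial cannot isolate a product effect in any case, rescue use is already recorded in the diary, and handling of intercurrent events is often left to a separate analysis plan. True, but the uncertainty about treatment at entry lies in the protocol's own text and adds an avoidable source of misattribution.

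**Conclusion.** The concern holds as an ambiguity with consequences. The protocol does not state whether corticosteroid may begin at the screening/baseline visit. If it does begin there, the before-after comparison counts its effect as product improvement. Whether this would happen, and in how many children, cannot be told from the document, so the size of the bias is unknown. Under the stated assumptions an inert product would reach significance on SCORAD about 31% to 80% of the time for a 5-point shift, and 7% to 13% for a 1.5-point shift. These figures show only that a moderate steroid contribution would be enough to matter. It should be corrected, since it touches the attribution of every efficacy endpoint.

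**What to change.** 1. Reconcile 9.1.6.7, 9.1.5.5 and 9.1.10.6 so that the protocol states one role for corticosteroid at entry, and say how 9.1.6.8 and 9.1.7.5 apply to steroid the protocol permits. Which rule to adopt is for the investigators; this review does not choose.
2. Record the date of every steroid start relative to the baseline scores, including any prescribed at entry. The diary in 9.1.10.5 asks for rescue treatment and deviations, and a steroid prescribed at entry might be entered as neither.
3. Report the IGA change overall, together with an analysis that does not credit improvement after steroid use to the product, for example by counting assessments after steroid use as not improved. Label any breakdown by steroid use as descriptive: it conditions on a post-baseline event, and under flare-only use the users are the children who worsened.
4. If the reconciled text has all children starting a steroid at entry, no analysis of one arm can separate the two, and the conclusion should be worded as the effect of product and steroid together.

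The cost is protocol wording, one extra recorded date, one additional analysis, and possibly a less favourable estimate.
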